2. INTRODUCTION

Participants will be enrolled from both active and placebo arms of qualifying efgartigimod studies in adult patients with pSS. The protocol will be amended to add additional studies at a later date.

In qualifying study ARGX-113-2106, the efficacy and safety of efgartigimod in adult patients with pSS was evaluated using a randomized, double-blinded, placebo-controlled study design. Participants were randomized to receive efgartigimod IV 10 mg/kg or matching placebo in a 2:1 ratio. The IMP (efgartigimod or matching placebo) was administered during the treatment period in approximately 1-hour IV infusion QW by site or a home nurse. The final dose was administered at week 23. At week 24, eligible participants from ARGX-113-2106 may roll over into the present single-arm OLE study: ARGX-113-2211.

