4. STUDY DESIGN

4.1. Overall Design

Study ARGX-113-2211 is a long-term, single-arm, open-label, multicenter extension of pSS-qualifying efgartigimod studies designed to evaluate the long-term safety of efgartigimod in adult patients with pSS. Participants will be enrolled from both active and placebo arms of qualifying efgartigimod studies and receive efgartigimod IV 10 mg/kg over 48 weeks in the extension study without knowledge of their treatment assigned in the qualifying study. To be eligible to enroll in this study, participants must have completed the treatment period of the qualifying study and must not have permanently discontinued the IMP in that study.

Participants will receive efgartigimod 10 mg/kg by IV infusion either Q2W or QW. The dosing regimen is based on whether the participant is a responder or nonresponder on day 1. Participants will be considered as responders if they have a reduction in clinESSDAI score of ≥ 3 points from baseline (ie, the final visit of a previous qualifying study) and/or a change in score that reclassifies their disease from moderate severity (clinESSDAI ≥ 5) to mild severity (clinESSDAI < 5). Participants will be considered as nonresponders if they do not have a reduction in clinESSDAI score of ≥ 3 points from baseline and/or did not reach a clinESSDAI < 5 . ClinESSDAI assessments to determine responder status using the baseline will be conducted on day 1 and weeks 16 and 24. Responders will receive IV infusions Q2W. Nonresponders will receive an infusion QW until such time that they are considered to be responders. If a participant is not a responder at week 24, they will be evaluated by the PI for therapeutic failure:

- Therapeutic failure - the participant will discontinue study treatment
- Not a therapeutic failure - the participant will continue QW dosing regimen. ClinESSDAI will be conducted at weeks 32, 36, 40, and 44 until confirming responder status and switching to Q2W dosing regimen. The PI will continue to evaluate the participant for therapeutic failure

If the participant and/or investigator consider there to be a reduction in therapeutic effect once the patient has switched to Q2W, the participant will return for an unscheduled visit during which a clinESSDAI, a blood sampling for PK and ADA will be collected.

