If there has been an increase in clinESSDAI score of ≥ 3 points and/or a change in score that reclassifies their disease from mild severity to moderate severity the participant will revert to QW dosing regimen and will remain on this dose regimen for the remainder of the treatment period.

IMP infusions must occur at the site for a minimum of 3 consecutive visits (for QW dosing regimen: baseline visit and the week 1 and 2 visits; for Q2W dosing regimen: baseline visit and the week 2 and 4 visits) before home infusions are allowed. If doses are missed at 1 or more of these visits, then dosing at subsequent visits will also be on-site. IMP administration at home will not commence until after 3 consecutive doses have been administered on-site.

Participants will return for a follow-up visit approximately 56 days after the final IMP administration.

The study's primary objective is to assess the long-term safety of efgartigimod in participants with pSS. The primary outcome of this study will be the incidence and severity of AEs and AESIs, the incidence of SAEs, changes in laboratory test results, vital signs, and ECG results. Additional assessments will be conducted, and blood samples will be collected to assess the effectiveness of efgartigimod at treating pSS, the PD effect of efgartigimod, and the immunogenicity of efgartigimod. Blood samples will also be collected to monitor the concentration of efgartigimod in blood over time.

A minimum of 10 study site visits over the 48-week treatment period and 56-day follow-up period are planned (baseline, weeks 1 [for QW regimen], 2, 4, 8, 12, 16, 24, 36, 48, and the SFV); all other visits (except for the first 3 consecutive visits) may be conducted by home health care service, or telemedicine visits.

The maximum length of time a participant can be in the study is approximately 56 weeks (48 weeks treatment plus 8 weeks of follow-up).

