9.2. Analysis Sets

The following analysis sets are defined:

Analysis set	Description
Full analysis set (FAS)	All enrolled subjects in the OLE study.
Safety set	All FAS subjects who have been administered study treatment during the OLE.

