9.3.4. Exploratory Endpoints Analysis

To explore the effect of efgartigimod on clinical pSS, glandular measures and patient-reported outcomes, serum and blood biomarkers the following analysis will be performed:

- The proportion along with an exact 90% CI of adjusted CRESS (without serology item) will be presented at week 24 and week 48
- Change from OLE baseline in activity of individual ESSDAI domains score, Hocevar score, Schirmer's test score, OSS score, MFI score, physical component and mental component scores of SF-36, PGA score, individual ESSPRI score, EQ-5D-5L utilities score, VAS score will be summarized descriptively at week 24 and week 48. Observed data will also be summarized at OLE baseline, week 24 and week 48

- Percentage change from OLE baseline scores of SWSF, UWSF will be summarized descriptively at week 24 and week 48. Observed data will also be summarized at OLE baseline, week 24 and week 48
- Observed data for response in salivary gland function and tear gland function (CRESS) and PASS score will be summarized descriptively at OLE baseline, week 24 and week 48
- CCI

- Counts and percentages of number of subjects who are on Q2W and QW dosing regimen will be presented at each scheduled visit
- Counts and percentage of the number of subjects with different clinESSDAI scores will be presented by each scheduled visit and the subgroups
- Time from first infusion to revert to QW dosing regimen will be analyzed using a Kaplan-Meier (KM) method. Summary statistics will include the upper and lower quartiles of duration (days) with 95% confidence interval, median duration (days), 95% confidence interval for median duration (days). KM probability of staying on Q2W dosing regimen will also be presented

All the primary, secondary and exploratory analysis will be based on the FAS.

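### The Kaplan-Meier curve for staying on Q2W counts time on QW as event-free, and the SAP's dosing-regimen subgroups overlap

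*Protocol*

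**What the plan says.** **Kaplan-Meier analysis (Protocol 9.3.4).** The protocol plans: "Time from first infusion to revert to QW dosing regimen will be analyzed using a Kaplan-Meier (KM) method". The summary includes the median and the "upper and lower quartiles of duration (days) with 95% confidence interval", and "KM probability of staying on Q2W dosing regimen will also be presented". The section ends: "All the primary, secondary and exploratory analysis will be based on the FAS". Protocol 9.2 defines the FAS as "All enrolled subjects in the OLE study".

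**Who is on Q2W, and when (Protocol 4.1 and Table 1 footnotes).** "Nonresponders will receive an infusion QW until such time that they are considered to be responders". The switch points are day 1, week 16 and week 24. A week-24 nonresponder who is not judged a therapeutic failure is reassessed at weeks 32, 36, 40 and 44. If a participant on Q2W later meets the worsening criterion, "the participant will revert to QW dosing regimen and will remain on this dose regimen for the remainder of the treatment period".

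**Regimen subgroups (SAP 13.1.5).** Change in clinESSDAI and ESSDAI is also summarised in three subgroups described as mutually exclusive: QW throughout; any switch from QW to Q2W; any switch from Q2W to QW. No precedence rule is given.

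**Exposure classes (SAP section 11, Table D).** There are four: QW throughout, Q2W throughout, Q2W to QW (SQW) and QW to Q2W (SQ2W). More detail is left to the ADaM specifications, depending on the data received.

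The visible SAP has no Kaplan-Meier text. SAP 13.2 and 13.3 are redacted, and SAP 3.4 lists only the dropped biomarker analysis as a change from the protocol.

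**The concern.** A participant on QW is not at risk of reverting to QW. If the clock starts at the first OLE infusion and all enrolled participants are in the risk set, every week spent on QW before a first Q2W dose counts as a week successfully kept on Q2W. This is immortal time, and it favours the less frequent regimen. The quartiles and median of duration are lengthened in the same way.

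Protocol 4.3 says Q2W was chosen for responders to see whether efficacy holds with fewer infusions. This curve is the visible time-to-event analysis of that question.

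In the subgroup summaries, the participants whose placement is unclear are those who reverted, so the placement rule affects how each regimen group's disease activity looks. With about 30 participants, moving a few of them could change a subgroup mean noticeably.

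**Working it through.** The plan gives no figure to reproduce, so the check covers direction, illustrative size and subgroup membership.

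**1. Direction.** Let S(t) be the probability of still being on Q2W t weeks after the first Q2W dose. On the first-infusion clock, a participant who starts Q2W after s weeks contributes S(t − s), which is at least S(t). One who never starts contributes no event. The averaged curve is therefore never below S(t). It lies above S(t) once reversions occur and anyone starts late or never.

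**2. Size at week 24 (assumed inputs).** Take a constant reversion hazard, S(t) = p^(t/24), a share d starting Q2W on day 1, and no dropout before week 24. Therapeutic failure is first assessed at week 24, so its censoring does not affect these figures.

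- Low end, all others start at week 16: d·S(24) + (1 − d)·S(8)
- High end, no other starts before week 24: d·S(24) + (1 − d)·1

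For p = 0.70, S(8) = 0.70^(1/3) = 0.888.

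| Share on Q2W from day 1 | True | Estimate as written |
|---|---|---|
| 100% | 0.700 | 0.700 |
| 70% | 0.700 | 0.49 + 0.3 × 0.888 = 0.756, to 0.790 |
| 50% | 0.700 | 0.35 + 0.5 × 0.888 = 0.794, to 0.850 |
| 0% | 0.700 | 0.888 to 1.000 |

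With d = 0.5, the estimate is 0.722 to 0.800 for p = 0.60 and 0.864 to 0.900 for p = 0.80.

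**3. Lower quartile of duration (p = 0.70).** True value: 24 × ln 0.75 / ln 0.70 = 19.4 weeks, or 136 days. With half on Q2W from day 1 and half from week 16, solving 0.5·S(t) + 0.5·S(t − 16) = 0.75 gives 27.8 weeks, or 195 days.

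**4. Unequal hazards.** Assume 50% start on day 1, 20% at week 16, 10% at week 24 and 20% never. Let true 24-week retention be 70% in day-1 starters and 40% in later starters. As written: 0.35 + 0.2 × 0.40^(1/3) + 0.1 + 0.2 = 0.797. From first Q2W dose: (0.5 × 0.70 + 0.3 × 0.40)/0.8 = 0.588. With 70% and 90% the pair is 0.843 and 0.775; with 90% and 50% it is 0.909 and 0.750.

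**5. Simulation at the planned size.** 30 participants (15 on Q2W from day 1, 8 from week 16, 7 never), p = 0.70, 4000 runs. The 7 were censored at week 24 and the others at week 46. Mean week-24 estimate as written: 0.820 (SD 0.066). From first Q2W infusion in those who receive it: 0.701 (SD 0.096).

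**6. Subgroup membership.** The parent-study treatment "was administered during the treatment period in approximately 1-hour IV infusion QW by site or a home nurse", and both the protocol schema and Table D's labels describe a day-1 Q2W start as a switch. Both readings are shown.

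| OLE path | SAP 13.1.5, OLE dosing only | SAP 13.1.5, parent QW counted | Table D |
|---|---|---|---|
| QW | QW throughout | QW throughout | QW |
| Q2W | none | to Q2W | Q2W |
| QW, Q2W | to Q2W | to Q2W | SQ2W |
| Q2W, QW | back to QW | to Q2W and back to QW | SQW |
| QW, Q2W, QW | to Q2W and back to QW | to Q2W and back to QW | none |

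Protocol 4.1 permits the last path. Under either reading the groups are not mutually exclusive, and under the first they also leave out participants on Q2W throughout.

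**The case against.** The strongest objection is that the governing text may be unseen. The protocol leaves technical detail to the SAP, and the redacted exploratory sections are where origin, risk set and censoring would be fixed. The FAS sentence also cannot be taken literally: an enrolled but undosed participant has no first infusion, and the SAP already analyses safety in the SAF. Since reverting and staying both presuppose being on Q2W, a restricted risk set may have been intended. This limits the Kaplan-Meier point to the protocol wording. It does not remove it, because that wording names the first infusion and restricts nothing.

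It is also fair that the size is wholly assumed, that the bias is zero if nobody reverts, that counts on each regimen by visit will show the start mix, and that nothing here is inferential. All of that stands.

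On the subgroups, the name of the third group suggests where reverters belong, and the secondary endpoint itself is the overall change, with the regimen split an added summary. Table D mainly serves exposure, which is largely summarised across regimens, and the ADaM specification is not dated. These points lower the stakes, but the overlap is real and the visible text does not resolve it.

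**Conclusion.** The concern holds. As the protocol is written, the curve overstates retention on Q2W whenever reversions occur and some participants start Q2W late or never. The direction follows from the design. The size does not: under an assumed true 24-week retention of 70%, the overstatement is about 6 to 9 points if 70% start on day 1, and 9 to 15 points if half do.

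The day-1 share is itself unsettled. Protocol 4.1 takes the responder baseline as the final visit of the qualifying study, while the synopsis and schema use that study's baseline. These passages must be reconciled.

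The subgroup overlap and the missing Table D class rest on visible SAP text and need no assumption. Everything affected is descriptive, and the primary safety conclusion does not change. The changes should still be made, because the curve errs in favour of the less frequent regimen.

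**What to change.** **Kaplan-Meier, in the protocol and SAP.** Restrict the analysis to participants with at least one Q2W infusion, set time zero at the first Q2W infusion, take reversion to QW as the event, and censor at end of treatment. Report how many stopped treatment while on Q2W and why, since censoring those who stopped for worsening would itself flatter the curve. If the redacted SAP text already sets this origin and risk set, align the protocol wording with it.

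**Subgroups, in SAP 13.1.5 and Table D.** Assign each participant once by full OLE path: QW throughout; Q2W from day 1 and kept; QW to Q2W and kept; any reversion from Q2W to QW, including QW to Q2W to QW. Fix the rule in the SAP rather than in the ADaM specifications. If three groups are preferred, state the precedence and say where participants on Q2W from day 1 belong.

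**Cost.** Wording and minor programming, using dosing dates already collected. The risk set becomes smaller and the curve less favourable and less precise: in the simulation above, the SD of the 24-week estimate rises from about 0.07 to 0.10.

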1.2. Schema

Abbreviations: D = day; IV = intravenous; QW = once weekly; Q2W = every 2 weeks; Wk = week.

^a QW or Q2W dosing regimen depending on responder status. Responders (defined as participants with a decrease in clinESSDAI of ≥ 3 points from baseline of qualifying study or who have a change clinESSDAI score that reclassifies their disease from moderate severity to mild severity) will be switched from QW to Q2W dosing regimen. Nonresponders will remain on QW dosing regimen. Switch points (ie, timepoints where clinESSDAI are conducted to determine responder status) will occur on day 1, week 16, and week 24. If a participant is not a responder at week 24, they will be evaluated by the PI for therapeutic failure. If not considered a therapeutic failure, the participant will continue QW dosing regimen and will return at weeks 32, 36, 40 and 44 for a clinESSDAI assessment until confirming the responder status and switching to Q2W dosing regimen or PI considers the participant to be a therapeutic failure. For QW regimen, the final dose will be administered at week 47. For Q2W regimen, the final dose will be administered at week 46.

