7.1. Discontinuation of IMP

7.1.1. Permanent Discontinuation

Permanent discontinuation of IMP occurs when the participant stops receiving the IMP before the end of the study, does not resume receiving IMP, and does not withdraw informed consent.

The investigator will document the primary reason for early discontinuation of IMP.

Participants who permanently discontinue IMP will complete the EDV.

The study sites will attempt to perform the EDV within 7 days after the participant's final IMP administration. The SFV will occur 56 ± 3 days after the participant's final IMP administration.

Additionally, the following circumstances will result in the permanent discontinuation of IMP:

- The participant becomes pregnant or intends to become pregnant (see Section 8.3.5)
- The investigator considers discontinuing IMP is in the participant's best interest (the sponsor will be informed)
- The participant develops an SAE or AE that contraindicates further administration of IMP in the investigator's opinion or an AE of CTCAE severity grade 4 that is considered related to IMP by the sponsor
- The participant develops a new or recurrent malignancy except for basal cell carcinoma of the skin, regardless of relationship to IMP
- The participant receives a prohibited medication or substance (Section 6.9)

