9.5. Sample Size Determination

No formal sample size calculation has been planned for this phase 2 OLE study. Up to approximately 30 subjects who have completed the efgartigimod pSS studies will be enrolled for the OLE study.

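### Protocol 9.3.4 counts only reversion to QW as the event but labels the Kaplan-Meier estimate as staying on Q2W; how a permanent stop of IMP while on Q2W is handled is not stated in the readable text

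*Protocol*

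**What the plan says.** Protocol 9.3.4 defines the variable and the method in one sentence: "Time from first infusion to revert to QW dosing regimen will be analyzed using a Kaplan-Meier (KM) method". It then lists the outputs: "Summary statistics will include the upper and lower quartiles of duration (days) with 95% confidence interval", the median with its interval, and finally "KM probability of staying on Q2W dosing regimen will also be presented". No event other than reversion is named, and the section gives no censoring rule. It closes with "All the primary, secondary and exploratory analysis will be based on the FAS".

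Protocol 4.1 makes reversion depend on a worsening in clinESSDAI found at an unscheduled visit, so only a participant still on treatment can revert. Protocol 7.1.1 treats a permanent stop of IMP as a separate outcome. Under the words "the following circumstances will result in the permanent discontinuation of IMP" it lists pregnancy, certain adverse events, malignancy, prohibited medication and the investigator's judgement. None of these depends on the dosing regimen, so all can occur on Q2W.

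The SAP's regimen classes (Section 11, Table D) are each defined by the regimen at week 48, and none describes a participant who stopped while on Q2W. The SAP's exploratory efficacy sections, from 13.2 onward, are redacted.

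**The concern.** Staying on Q2W can end in two ways: reverting to QW, or ending IMP. The named event covers only the first. A standard Kaplan-Meier analysis censors everyone who leaves by the second route and so treats them as if they went on facing the same reversion risk as those still on Q2W. In fact they can no longer revert, and they are no longer on Q2W. For reversion, a permanent stop is a competing event. For staying on Q2W, it is itself an exit.

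Protocol 4.3 gives the reason for the Q2W regimen as finding out whether less frequent dosing can maintain efficacy. This curve is the only time-to-event summary of that question in the readable text. A figure labelled as staying on Q2W will be taken as the share of participants who remained on the regimen. In a study described as "Up to approximately 30 subjects who have completed the efgartigimod pSS studies will be enrolled for the OLE study", a few stops can move that share noticeably.

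**Working it through.** **Inputs from the documents.** The event is reversion to QW, and the label is staying on Q2W (Protocol 9.3.4). Up to about 30 participants are enrolled (9.5); the number on Q2W is not given. Planned follow-up on the regimen is bounded by "For Q2W regimen, the final dose will be administered at week 46" (1.2). No reversion rate, stop rate or Kaplan-Meier figure is stated, so there is nothing to reproduce and every rate below is an assumption.

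**Quantities, among participants on Q2W.** Let r be the proportion who revert by the end of treatment and s the proportion who permanently stop while on Q2W.

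- Still on Q2W: 1 − r − s.
- Never reverted: 1 − r.
- Kaplan-Meier with stops censored, constant cause-specific hazards: (1 − r − s)^(r/(r+s)).

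The exponent is at most 1, so the Kaplan-Meier value is never below 1 − r − s, and it equals it only when s = 0. If stopped participants were instead kept in the risk set to the end, the curve would finish at 1 − r, which is higher still. Only counting the stop as an exit gives the labelled quantity.

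**Results over the assumed range.**

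| r | s | KM, stops censored | Still on Q2W | Excess (points) | Shortfall against never reverted (points) |
|---|---|---|---|---|---|
| 20% | 0% | 80.0% | 80.0% | 0 | 0 |
| 20% | 8% | 79.1% | 72.0% | 7.1 | 0.9 |
| 20% | 17% | 77.9% | 63.0% | 14.9 | 2.1 |
| 30% | 8% | 68.6% | 62.0% | 6.6 | 1.4 |
| 30% | 17% | 66.7% | 53.0% | 13.7 | 3.3 |

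For example, in the third row 0.63^(0.20/0.37) = 0.779, and 0.779 − 0.630 = 0.149.

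**Where 8% to 17% comes from.** These are the actual proportions stopping that correspond to net risks of 10% and 20% when the net reversion risk is 30%. With hazards −ln 0.70 = 0.357 and −ln 0.90 = 0.105, the proportion stopping is 0.105/0.462 × (1 − 0.63) = 8.4%. Kaplan-Meier gives 70% against 0.70 × 0.90 = 63%, a gap of 7 points. With a 20% net stop risk the hazard is 0.223, the proportion stopping is 0.223/0.580 × (1 − 0.56) = 16.9%, and the gap is 70% − 56% = 14 points.

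**A small cohort.** Take 20 participants on Q2W, with reversions on days 113, 169, 190 and 253 and stops on days 60, 140 and 230.

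- Risk sets at the reversions are 19, 17, 16 and 14. Kaplan-Meier: (18/19)(16/17)(15/16)(13/14) = 77.6%.
- Still on Q2W: 13/20 = 65.0%.
- Never reverted: 16/20 = 80.0%.
- Greenwood standard error: 0.776 × √(1/342 + 1/272 + 1/240 + 1/182) = 0.099. The gap of 12.6 points is about 1.3 standard errors.
- Moving all the stops before or after all the reversions changes the Kaplan-Meier value only between 76.5% and 80.0%.

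**The case against.** **The rule may exist.** Protocol Section 9 leaves technical detail to the SAP, and the SAP section that would hold it is redacted. A reader might infer that the plan censors these participants. The documents do not say so; it is an inference from the event definition and standard practice. This objection stands against any claim that censoring is planned. It does not remove the mismatch between event and label, which is in readable protocol text.

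**Loss of effect on Q2W is largely captured.** A reader might infer that participants for whom Q2W failed drop out of the curve and flatter the regimen. The main pathway for worsening on Q2W is reversion to QW, which is the event and does lower the curve. Week-24 therapeutic failure ("Therapeutic failure - the participant will discontinue study treatment") is assessed in nonresponders, who are described as continuing QW if they are not failures, so it is mainly a stop from QW. SAP Table D does foresee a Q2W participant becoming a non-responder at week 24, so a failure stop from Q2W is not strictly excluded, but it adds little.

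**Time to reversion is a legitimate target.** Pregnancy or a prohibited medication says little about whether Q2W maintains efficacy, and no estimand is defined. That is fair. It argues for labelling the curve as time to reversion; it does not support calling it staying on Q2W.

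**Other outputs show part of the picture.** Protocol 9.3.4 also plans counts and percentages on each regimen by visit, and SAP 8.1 tabulates discontinuations with reasons. The counts help. The percentages may not, because SAP 7.2 leaves missing values out of denominators.

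**Conclusion.** The point holds as a mismatch between the named event and the label. If stops are handled as standard Kaplan-Meier would handle them, the figure labelled as staying on Q2W overstates the share still on Q2W as soon as one participant stops while on it. The direction follows from the algebra; the size cannot be known from the documents. The figure of roughly 7 to 15 points rests on assumed reversion of 20% to 30%, assumed stopping on Q2W of about 8% to 17%, constant hazards, and a risk set made up of participants on Q2W.

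A reader might go further and call the planned probability simply too high. That is not supported: there is no error if nobody stops on Q2W, and against the reading of never having reverted the same estimate is about 1 to 3 points too low over this range. One curve cannot serve both meanings. The severity is minor, because the output is exploratory and descriptive and the protocol rules out inferential use of the results.

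**What to change.** First check the redacted SAP section. If it already says how a permanent stop on Q2W is handled, confirm that and align Protocol 9.3.4. If not:

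- For staying on Q2W, define the event as the first of reversion to QW or permanent end of IMP for any reason. Name consent withdrawal explicitly, because Protocol 7.1.1 leaves it out of permanent discontinuation. Censor at the end of the treatment period, at data cut-off, or at the last known dosing date for participants lost to follow-up.
- Report reversion to QW separately as a cumulative incidence (Aalen-Johansen), with permanent end of IMP as the competing event.
- If only the existing curve is kept, label it as time to reversion and not as staying on Q2W.

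The cost is a few lines of wording and one extra output. No new data are needed, since SAP 8.1 already tabulates discontinuations and SAP Section 11 already lists dosing. The downside is a less favourable figure for staying on Q2W.
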